7.1 Study design

This is a interventional, multicenter, non-randomized, parallel-group, opened designed study lasting during 12 months for approximately 130 patients with type 2 diabetes and obesity.

In spite of interventional study status, the drug therapy administration is carried out strictly in accordance with the approved instructions for medical use, only with the registered indications and in accordance with appropriate clinical practice. The decision on the drug therapy administration should be based only on the medical indications and on the judgment of a physician, but should not be dependent on the decision to include the patient in the study. The project includes unique method of weight management, specifically designed for the patients with type 2 diabetes. It includes five components:

- 1) Structured modified diet change;
- 2) Balanced and personalized physical exercises;
- 3) Cognitive behavioral support;
- 4) Intensive interactive medical assistance;
- 5) Group education.

An outline of the study design is presented in Figure 7-1. The full study lasts 12 months (1 month constitutes 4 weeks or 28 days). Patients from active group are monitored intensely during the first three months (on a weekly basis with acceptable window of visits +/- 1 day)

Nutritionist consultation	X																			
TE doctor/fitness trainer consultation	X																			
Demographic data ¹	X																			
Diabetes history ²	X																			
Relevant medical history / current medical condition ³	X																			
Group classes with endocrinologist		X	X	X	X	X	X	X	X	X	X	X	X							
Group classes with psychologist		X	X	X	X	X	X	X	X	X	X	X	X							
Group classes of nutrition		X	X	X	X	X	X	X	X	X	X	X	X							
Group classes of medical physical culture		X	X	X	X	X	X	X	X	X	X	X	X							
Physical examination	X				X				X			X	X	X	X	X	X	X	X	X
HbA _{1c}	X											X			X			X		X
FPG	X	X	X	X	X	X	X	X	X	X	X	X	X	X	X	X	X	X	X	X
Weight	X	X	X	X	X	X	X	X	X	X	X	X	X	X	X	X	X	X	X	X
BMI	X				X				X				X	X	X	X	X	X	X	X
Waist circumference	X				X				X				X	X	X	X	X	X	X	X
Waist/hip ratio	X				X				X				X	X	X	X	X	X	X	X
Blood pressure	X	X	X	X	X	X	X	X	X	X	X	X	X	X	X	X	X	X	X	X
ECG (standard 12-lead)	X												X							X
General blood pressure ⁴	X												X							X
Clinical blood chemistry ⁵	X												X							X
Urinalysis ⁶	X												X							X
AEs	X	X	X	X	X	X	X	X	X	X	X	X	X	X	X	X	X	X	X	X
Diaries of self-control	X	X	X	X	X	X	X	X	X	X	X	X	X	X	X	X	X	X	X	X

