Hypoglycemia questionnaires	X														X					X
Scale of Borg ⁷		X																		X
HE supply form	X				X				X				X	X	X	X	X	X	X	X

*Acceptable deviation for weekly planned visits (visits 2-13) is +/-1 day from the planned date, monthly visits (visits 14-22) is +/- 3 days from the planned date.

¹ Demographic indicators: age, gender, race.

² Date of diagnosis of diabetes, clinical symptoms.

Therapy for diabetes: insulin (type, dosage), insulin+oral hypoglycemic therapy (type, dosage), sulphonylurea (type, dosage), glinide (type, dosage), metformin (dosage), TZD (dosage), DPP4 (type, dosage), GLP1 (type, dosage), other type of treatment.

Complications of diabetes: cardio-vascular diseases, strokes, retinopathy, neuropathy, nephropathy, diabetic foot, other.

³ Concomitant diseases (cardio-vascular diseases, hypertension, eye diseases, vascular diseases of the brain, gastrointestinal tract diseases, respiratory diseases, liver and bile ducts diseases, kidney diseases, blood diseases, etc.)

⁴ General blood test: hemoglobin, leukocytes (+formula), erythrocytes, thrombocytes, ESR.

⁵ Clinical blood test: crude protein, cholesterol, lipids of low and high density, triglycerides, ALT, AST, KPhK, creatinine, GFR.

⁶ Urine analysis: color, transparency, relative density, traces of protein, sugar in urine, ketone bodies.

⁷ Scale of Borg (scale of individual perception of physical training) is part of Information card (Appendix 8).

Study period and parallel group study design allows achieving of primary end point.

The control group indicators should be coordinated with the indicators of patients in active group. The following should be taken into account when active group is being formed: correspondence of BMI and baseline HbA1c. The decision on whether the patient is included in active or control group is made by the doctor.

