10.3 Patient demographics/other baseline characteristics

All Baseline assessments should be performed prior to first study treatment administration. Patient demographic data to be collected on all patients include: date of birth, sex, race, ethnicity, and child-bearing potential (for females only), see the comments to the table 7-1.

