- 1) Structured modified diet change;
- 2) Balanced and personalized physical exercises;
- 3) Cognitive behavioral support;
- 4) Intensive interactive medical assistance;
- 5) Group education.

The total duration of the study for each patient is 12 months (1 month is equal to 4 weeks or 28 days). Patients from active group will be monitored intensively during the first three months (weekly, with allowed visit window of +/- 1 day) and then will continue to participate in the study for the remaining 9 months. After the first 13 weeks, monthly (+/- 3 days) assessments of weight and health status of patients from the active group will be performed. Key laboratory parameters will be measured and the physician will make a decision on whether the diabetes therapy should be adjusted as the patient's weight is reduced.

3 Sample size determination

The primary objective of this study is to assess the change of weight from baseline, in patients with T2DM at 12 months in comparison to the change in weight from baseline in the parallel cohort. Sample size was calculated based on weight changes observed in Why Wait study conducted at the Joslin center. The average weight loss observed at the end of 12 months was 8%. Given that baseline criteria and translation of the program can be different in its implementation in Russia, we have assumed an achievable change in weight as 5%. Significant reduction of body weight in the control group is not anticipated. The sample size (with the possible dropout of 20%) of 100 patients in active group and 30 patients in parallel cohort is sufficient to provide 80% power to detect a significant difference (significance level is $\alpha=0.05$) between values in the two groups.

4 Randomization and blinding

Not applicable.

5 Efficacy assessment

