6.2 Exclusion criteria

Patients fulfilling any of the following criteria are not eligible for inclusion in this study:

1. Pregnant or nursing (lactating) women, where pregnancy is defined as the state of a female after conception and until the termination of gestation.
2. Type 1 diabetes
3. Proliferative retinopathy, hemorrhage and disinsertion of retina
4. Renal impairment: serum creatinine >1.5 mg/dL, creatinine clearance < 40 ml/min and/or proteinuria.
5. The lack of ability to perform the physical exercises due to the orthopedic or cardiovascular disorders *
6. Chronic alcoholism, acute alcoholic intoxication

* - the criterion is applicable only for the active group.

7 Population determination for statistical analysis

- All enrolled patients: all patients who signed informed consent for inclusion in the study. The population will be used for the disposition data summaries and listings.
- Safety Population: all patients of the active group included in the study, who started participating in the lifestyle correction program, and all patients of the

control group for whom the observation was started. The population will be used to summarize adverse events and other safety parameters.

- Full Analysis Set (FAS): all patients who provided baseline data and data to evaluate at least one efficacy parameter after the onset of observation. The population will be used for efficacy analyses.
- Per Protocol Set (PP): all FAS patients who did not have any major protocol deviations. The population was used to analyze the primary endpoint (sensitivity analysis).

The patient can be excluded from the Per Protocol Set for the following reasons:

- did not attend more than 3 consecutive classes in the active group;
- missed at least 50% classes of the program;
- did not provide data for the estimation of the primary endpoint.

8 General considerations

The latest available estimates before the start of the program for the active group and data from the Visit 1 for the control group will be used as the baseline values for the analysis of quantitative efficacy and safety parameters. The baseline visit is Visit 2 (Week 1) for the active group and Visit 1 for the control group.

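### Baseline is Visit 2 for the active group but Visit 1 for controls, program start is undefined, and no planned analysis uses a common baseline

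*SAP*

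**What the plan says.** SAP section 8 (General considerations) gives two statements on baseline. The first sets the values to be used: "The latest available estimates before the start of the program for the active group and data from the Visit 1 for the control group". The second names the visits: "The baseline visit is Visit 2 (Week 1) for the active group and Visit 1 for the control group".

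In the active-group schedule under Protocol 7.1, the rows "Nutritionist consultation" and "TE doctor/fitness trainer consultation" are each marked once, in the first column, alongside demographics and medical history. Group classes begin in the second column. Weight, FPG and blood pressure are marked in both columns. The self-control diary is also marked from the first column. The schedule's footnote reads "Acceptable deviation for weekly planned visits (visits 2-13) is +/-1 day from the planned date", so Visit 2 is the first weekly visit and the first column is most naturally Visit 1.

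The SAP's list of five program components begins with "Structured modified diet change" and "Balanced and personalized physical exercises". Protocol 10.3 adds: "All Baseline assessments should be performed prior to first study treatment administration". It names no visit.

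The primary endpoint (SAP 5.1) is a loss of at least 5% from baseline at 12 months, compared between groups by adjusted logistic regression (SAP 12.1). The sensitivity analyses are the per-protocol set and a GEE model without imputation. Neither changes the baseline.

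**The concern.** The comparison is non-randomized, and the change score starts at a different point in each group. Controls are measured from their first visit. Active patients are measured from a visit about a week later, by which time they appear to have had individual diet and exercise consultations and to have started a diary. If these contacts already change behavior, part of the program's effect falls before the active baseline and is not counted.

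The endpoint makes this matter more than it would for a mean change. The assumed mean loss in the sample size section (5%) equals the responder threshold (5%). If losses are roughly normal, the threshold then sits where patients are most densely concentrated, and a small shift in baseline reclassifies a noticeable share of them.

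The baselines also differ within the active group. HbA1c and waist circumference are marked at Visit 1 but not Visit 2, so their changes run from Visit 1 while weight change runs from Visit 2.

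**Working it through.** **1. Do the two sentences of SAP 8 agree?** That depends on when the program starts.

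- If it starts with the first group class at Visit 2, and the Visit 2 weight is taken before that class, the last pre-program value is the Visit 2 weight. The sentences agree.
- If it starts with the Visit 1 consultations, the last pre-program value is the Visit 1 weight. The sentences conflict, and a Visit 2 baseline also sits badly with Protocol 10.3.

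The SAP does not settle this. Section 13 places the first Borg rating at Visit 1 and treats it as the rating from the start of the program. Section 11 counts treatment duration from the baseline visit but program duration from an initial visit, without saying whether the two are the same.

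**2. Inputs for an illustration.**

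- From the documents: threshold 5% (SAP 5.1); mean active loss 5%, no meaningful control loss, 100 and 30 patients, 20% dropout, 80% power, alpha 0.05 (SAP 3); no control dropout (SAP 6); target of at least 5% loss in the first three months (Protocol 10), a month being 4 weeks (Protocol 7.1).
- Assumed: the 5% mean is counted from Visit 1; losses are normal; SD is 5% or 8%; the Visit 1 to Visit 2 loss *d* is the same for every patient. The documents give neither an SD nor any value of *d*.

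Because no SD is stated, the planned sample size cannot be reproduced. Solving backwards for 80 active and 30 control patients, two-sided, gives SD = 5 / [(1.960 + 0.842) × √(1/80 + 1/30)] = 8.34%. The upper SD of 8% is therefore close to what the plan implies.

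**3. Responder rate.** With *d* as a fraction of Visit 1 weight, a 5% loss from Visit 2 requires a loss from Visit 1 of 1 − 0.95(1 − *d*) = 0.05 + 0.95*d*. With a mean of 5%, the responder rate is 1 − Φ(0.95*d*/SD).

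| *d* | Loss needed from Visit 1 | SD 5% | SD 8% |
|---|---|---|---|
| −0.5% (gain) | 4.53% | 53.8% | 52.4% |
| 0 | 5.00% | 50.0% | 50.0% |
| 0.42% | 5.40% | 46.8% | 48.0% |
| 0.5% | 5.48% | 46.2% | 47.6% |
| 1.0% | 5.95% | 42.5% | 45.3% |
| 1.5% | 6.43% | 38.8% | 42.9% |

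The 0.42% row is the protocol's target at an even pace: 5% / 12 weeks = 0.42% per week. The control rate does not depend on *d*.

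**4. Odds ratio and power, same assumptions.** Take control loss as normal with mean 0 and the same SD, so the control rate is 1 − Φ(5/SD). Power is Φ[(|pA − pC| − 1.96·SE0)/SE1], with SE0 from the pooled proportion, SE1 unpooled, and 80 and 30 patients.

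| SD | Control rate | *d* | Unadjusted OR | Power |
|---|---|---|---|---|
| 5% | 15.9% | 0 | 5.30 | 94% |
| 5% | 15.9% | 0.5% | 4.56 | 87.5% |
| 5% | 15.9% | 1.0% | 3.91 | 78% |
| 8.34% | 27.4% | 0 | 2.64 | 57% |
| 8.34% | 27.4% | 0.5% | 2.41 | 48% |
| 8.34% | 27.4% | 1.0% | 2.20 | 40% |

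These figures show sensitivity. They do not predict the trial's result.

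**The case against.** The strongest defense is that SAP 8 applies one conventional idea to each group: the last value before the intervention for active patients, and the value at the start of observation for controls. Protocol 10 describes the weight-reduction program in terms of group classes, and those start at Visit 2. Nothing readable says what the Visit 1 consultations contain; they could be assessment or clearance for exercise rather than advice. The SAP also recognizes a pre-program window elsewhere, since it leaves out active-group adverse events that began before the program. On that reading, Visit 2 satisfies Protocol 10.3 and the rule is defensible.

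The size is also uncertain. Early losses of 0.5 to 1.5% all exceed the protocol's average pace of 0.42% per week, which is a target for the period when classes are running. With no early change, nothing shifts. The schedule header is missing from the text available and its columns do not line up perfectly with the visit numbers, so the Visit 1 placement should be confirmed against the original table.

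All of this stands, and it limits the point. It does not remove the undefined program start, the different baseline visits in the two groups, or the lack of any analysis that would show whether the choice matters.

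A reader might go further and infer that the planned effect estimate is wrong, or that the asymmetry flatters the program. The documents support neither. The first holds only if the consultations start the program and weight changes before Visit 2. The second would need weight to rise between the visits. A reader might also stress that follow-up is 47 weeks in one group and 48 in the other. That assumes Week 48 is counted from inclusion, and the one-week difference is minor.

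**Conclusion.** The point holds as a between-group asymmetry combined with an undefined term. SAP 8 measures change from Visit 2 in active patients and Visit 1 in controls. It becomes internally inconsistent if the Visit 1 consultations count as program start. Any weight lost between the two visits would be removed from the active effect only, so the bias is conservative and does not threaten a positive finding. Its cost would be an understated effect and some loss of power in a comparison with 30 controls.

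The size cannot be known from the documents. Under the assumptions shown, the active responder rate falls by 2 to 3 points at the protocol's average pace, and by about 5 to 8 points if 1% is lost before Visit 2. It does not fall at all if weight is stable. The conclusion also rests on the first schedule column being Visit 1. The case for change is that a common baseline is cheap and removes an avoidable difference between non-randomized groups.

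**What to change.** In SAP section 8:

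- Define program start, and state whether the Visit 1 consultations are part of it.
- Use Visit 1 as baseline in both groups for weight (primary and secondary endpoints), FPG and blood pressure.
- Report the primary endpoint with the Visit 2 active baseline as a sensitivity analysis.

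If the sponsor prefers to keep Visit 2, the minimum is to define program start, state that the Visit 2 weight precedes the first class, and add an analysis of the primary endpoint from a common Visit 1 baseline.

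The cost is SAP wording and one more run of the primary model. The active schedule already collects Visit 1 weight, FPG and blood pressure, and the sample size is unchanged. The one drawback is that the active baseline becomes about a week older. HbA1c and waist circumference already use Visit 1, so the change also aligns the baselines within the active group.

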The Last observation carried forward (LOCF) approach will be used in FAS population (primary analysis) to impute missing values of the efficacy parameters using the last available measurement after the initiation of the studied program for active group and after the start of observation for the control group.

Descriptive statistics for quantitative variables will include mean, standard deviation, median, quartiles, minimum and maximum, and the number of observations. The maximum number of decimal places reported shall be 4 for any summary statistic.

Qualitative data will be presented in terms of the number of patients providing data at the relevant time point (n), frequency counts and percentages. Percentages will be calculated using n as denominator and will be presented to one decimal place.

9 Patient disposition

The following data on patient disposition will be provided for the All enrolled patients set:

- Number and proportion of patients in each population for statistical analysis;
- The number and proportion of patients enrolled in the study, as well as attended each study visit;
- Number and proportion of patients who discontinued prematurely (indicating the reasons for the discontinuation), as well as those who completed the study;
- Number and proportion of eligible patients.

10 Demographic and other baseline characteristics

The following demographic and other baseline characteristics will be tabulated and presented descriptively:

- Demographic characteristics (age, sex, race);
- Medical history (number (proportion) of patients with concomitant diseases);
- Duration of type 2 diabetes (months);
- Clinical manifestations of diabetes at the time of diagnosis and at the time of enrollment (the number (proportion) of patients with each of the clinical manifestations);
- Concomitant complications of diabetes (number (proportion) of patients with concomitant complications);
- Baseline body weight, height, body mass index;
- Baseline HbA1c% and fasting blood glucose (mmol/l).

Age will be calculated as the number of complete years between the date of birth of the patient and the date of signing the informed consent.

The body mass index (kg/m²) at each visit will be calculated as the ratio of body weight (kg) to the square of height (m) (Visit 1).

The duration of the disease will be calculated in years as (the date of the primary diagnosis of type II diabetes - the date of the informed consent + 1) / 365.25.

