If the date of the primary diagnosis is partial, the following imputation rules will be used to calculate the duration of the disease:

- If year is missing - no imputation (missing value);
- If month and day are missing, 1st of January will be used;
- If only day is missing, 1st day of the corresponding month will be used.

Medical history data will be coded using the Medical Dictionary for Regulatory Activities (MedDRA, version 19.0). Prior and concomitant therapy will be coded using the WHO DDE Dictionary (1st December 2016), including the ATC class and LLT (Lowest Level Term).

All demographic data, concomitant therapy, and medical history data will also be listed.

11 Treatment

Patients participating in this study will receive drug therapy for diabetes according to routine clinical practice, and there are no restrictions for the therapy because of patient's participation in this study.

The drugs are used in accordance with the instruction for medical use, only for registered indications and in accordance with routine clinical practice.

The duration of treatment will be calculated as the length of participation in the study (the date of study completion or date of the last visit - the date of the baseline visit + 1) / 7 (weeks).

The program duration will be calculated for the active group as the length of participation in the program (the date of the last visit during the program sessions - the date of the initial visit + 1) / 7 (weeks).

Information on the intake of hypoglycemic therapy during the study will be presented in the frequency tables by ATC class and Lowest Level Term.

The duration of treatment within the study and the length of the program in weeks will be tabulated using descriptive statistics for continuous variables. The number and percent of classes attended will be summarized.

The number and percentage of patients taking concomitant medications will also be presented in frequency tables by ATC class and Lowest Level Term.

12 Efficacy analysis

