18.1 List of Tables

Table 1.1 Patient disposition (All patients)

Table 2.1 Demographic and other baseline characteristics (FAS)

Table 2.2.1 Medical history (FAS)

Table 2.2.1 Clinical manifestations of diabetes at the time of diagnosis (FAS)

Table 2.2.2 Clinical manifestations of diabetes at the time of inclusion (FAS)

Table 2.2.3 Concomitant complications (FAS)

Table 2.3 Concomitant hypoglycemic therapy of diabetes (FAS)

Table 2.4 Other concomitant therapy (FAS)

Table 3.1 Duration of treatment and participation in the program (Safety Population)

Table 3.2 Attended classes (Safety Population, Active Group)

Table 4.1.1 Descriptive statistics for body weight values and their changes in percent and absolute units for study visits (FAS)

Table 4.1.2 Decrease in body weight by at least 5% compared to baseline values for study visits (FAS)

Table 4.1.3.1 Analysis of the primary endpoint - decrease in body weight by at least 5% compared to baseline values at 12 months of observation (FAS)

Table 4.1.3.2 Sensitivity analysis for primary end point (PP)

Table 4.1.3.3 Sensitivity analysis for the primary endpoint using GEE (FAS)

Table 4.1.4. Analysis of the decrease in body weight by at least 5% compared to baseline values at 3, 6, 9 months of observation (FAS)

Table 4.1.5 Decrease in body weight by at least 10% compared with baseline values for study visits (FAS)

Table 4.1.6. Analysis of the decrease in body weight by at least 10% compared to baseline values at 3, 6, 9 and 12 months of observation (FAS)

Table 4.1.7 Analysis of absolute changes in body weight compared to baseline values at 3, 6, 9 and 12 months of observation (FAS)

Table 4.1.8 Analysis of changes in body weight in % compared with baseline values at 3, 6, 9 and 12 months of observation (FAS)

Table 4.2.1 Descriptive statistics for body mass index values and their changes in percent and absolute units by study visits (FAS)

Table 4.2.2 Analysis of changes in body mass index compared to baseline values at 3, 6, 9 and 12 months of observation (FAS)

Table 4.3.1 Descriptive statistics for waist circumference values and their changes by study visits (FAS)

Table 4.3.2 Analysis of changes in WC compared to baseline values (FAS)

Table 4.3.3 Descriptive statistics for the values of the hip circumference and their changes by study visits (FAS)

Table 4.3.4 Descriptive statistics for the values of WHR ratio and their changes by study visits (FAS)

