18.2 List of Listing

- Listing 1.1 Disposition (All enrolled patients)
- Listing 1.2 Inclusion / exclusion criteria (All enrolled patients)
- Listing 1.3 Protocol deviations (All enrolled patients)
- Listing 1.4 Study visits (All enrolled patients)
- Listing 2.1 Demographic and other baseline characteristics (All enrolled patients)
- Listing 2.2 Medical history (All patients included)
- Listing 2.3 Clinical manifestations of diabetes (All enrolled patients)
- Listing 2.4 Concomitant complications (All enrolled patients)
- Listing 3.1 Concomitant hypoglycemic therapy (All enrolled patients)
- Listing 3.2 Concomitant therapy (All enrolled patients)
- Listing 3.3 Lifestyle program attendance (Safety Population, Active Group)
- Listing 4.1 Body weight and BMI dynamics (All enrolled patients)
- Listing 4.2 WC, HC, WHR dynamics (All enrolled patients)
- Listing 4.3 HbA1c and FBG dynamics (All enrolled patients)
- Listing 4.4 Vital signs dynamics (All enrolled patients)
- Listing 5.1 Adverse events (All patients included)
- Listing 5.2 Serious adverse events (All patients included)
- Listing 5.3 Adverse events leading to discontinuation (All enrolled patients)
- Listing 5.4 Fatal adverse events (All patients included)
- Listing 6.1 Biochemistry laboratory parameters dynamics (All enrolled patients)
- Listing 6.2 Hematology laboratory parameters dynamics (All enrolled patients)
- Listing 6.3 Clinical urinalysis parameters assessments dynamics (All enrolled patients)
- Listing 7 ECG results (All enrolled patients)
- Listing 8 Physical examination results (All enrolled patients)
- Listing 9.1 Questionnaire for hypoglycemia evaluation results (All enrolled patients)
- Listing 9.2 Individual perception of physical activity (Borg scale) results (All enrolled patients, active group)

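### The SAP's disease-duration formula subtracts the dates in the wrong order, giving negative durations, and the same section uses months in one place and years in another

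*SAP*

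**What the plan says.** SAP section 10 (Demographic and other baseline characteristics) lists "Duration of type 2 diabetes (months") among the variables to be tabulated. Further down, the same section says that duration is calculated in years and gives the formula "the date of the primary diagnosis of type II diabetes - the date of the informed consent + 1) / 365.25". The rules that follow deal only with partial diagnosis dates.

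The SAP defines two other durations, both in section 11 (Treatment):

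- duration of treatment: "the date of study completion or date of the last visit - the date of the baseline visit + 1) / 7"
- duration of the program: "the date of the last visit during the program sessions - the date of the initial visit + 1) / 7 (weeks"

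Section 8 sets the summaries: "Descriptive statistics for quantitative variables will include mean, standard deviation, median, quartiles, minimum and maximum, and the number of observations". The outputs whose titles match section 10 are "Table 2.1 Demographic and other baseline characteristics (FAS") and "Listing 2.1 Demographic and other baseline characteristics (All enrolled patients").

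Disease duration is also a covariate in the primary logistic regression (SAP section 12.1, Protocol section 13). It is a candidate covariate in the GEE sensitivity analysis, where it is kept if p < 0.1.

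**The concern.** Confirmed type 2 diabetes is an inclusion criterion (SAP section 6.1), so the diagnosis date normally precedes consent. The formula subtracts the later date from the earlier one and so returns a negative number for almost every patient. The two formulas in section 11 run later minus earlier, so the order in section 10 is not a convention of this SAP.

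The unit conflict is a separate fault. A negative duration is obviously wrong, but a value of 10 under a months heading looks plausible and could pass a quality check.

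What is at stake is the description of the groups. The study is not randomized, the physician decides the group, and the only matching criteria named explicitly are BMI and baseline HbA1c (Protocol section 8, SAP section 6). Duration is not one of them, yet the plan treats it as a potential confounder. Readers will look to the baseline table to see whether the groups differ on it.

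**Working it through.** **Inputs.** The formula and the months label come from SAP section 10, and the comparison formulas from SAP section 11. The documents give no numerical duration to reproduce. The calendar dates below are assumed, with consent on 1 March 2015.

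**Formulas.** Let n be the number of days from diagnosis to consent.

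- As written: W = (-n + 1) / 365.25
- Later minus earlier: T = (n + 1) / 365.25

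**Where the sign changes.** W is +0.0027 for n = 0, 0 for n = 1 and -0.0027 for n = 2. It is negative exactly when diagnosis is more than one day before consent.

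**Values.**

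| Diagnosis date | n (days) | As written (years) | Corrected (years) |
|---|---|---|---|
| 1 March 2014 | 365 | -0.997 | 1.002 |
| 1 March 2010 | 1826 | -4.997 | 5.002 |
| 1 March 2005 | 3652 | -9.996 | 10.001 |
| 1 March 1995 | 7305 | -19.997 | 20.003 |

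In the written order the added day shortens the magnitude instead of counting both end days. The sum of W and T is always 2 / 365.25 = 0.0055 years, so this part of the error is only two days.

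**Effect on the summary table.** Take five illustrative patients with histories of 1, 5, 10, 15 and 20 years, and take the quartiles as the second and fourth ordered values.

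| Statistic | As written | Corrected |
|---|---|---|
| Mean | -10.20 | 10.20 |
| Lower quartile | -15.00 | 5.00 |
| Upper quartile | -5.00 | 15.00 |
| Minimum | -20.00 | 1.00 |
| Maximum | -1.00 | 20.00 |

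The order of the statistics reverses along with the sign. Deleting the minus signs from a finished table would leave a minimum of 20 and a maximum of 1. The standard deviation does not change.

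**Unit.** The corrected 10-year value is 10.0014 × 12 = 120.02 months. Printing 10.00 under a months heading understates it by a factor of 12.

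**Effect on the models.** Because W = 2/365.25 - T, a term c × T in the linear predictor equals c × 2/365.25 - c × W. The constant goes into the intercept and the coefficient of duration changes sign. The group coefficient, its standard error, the odds ratio, the confidence interval and the p-value are unchanged. The p-value for duration is unchanged too, so the p < 0.1 screen in the GEE analysis selects the same covariates. Multiplying by 12 only rescales the duration coefficient.

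**Correction elsewhere.** None was found. Section 10 states no absolute value and no conversion to months. The partial-date rules do not touch the order of subtraction. SAP section 16 (Changes in the statistical analysis plan) does not mention duration. Protocol section 13 names disease duration as a covariate without giving a formula.

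**The case against.** The best reply is that this is a drafting slip that would reveal itself. Nearly every value would be negative, a programmer would see that at the first check, and the intent is clear from the word duration and from the two correctly ordered formulas in section 11. No inferential result depends on it. The mislabelled quartiles and extremes arise without negative signs only if someone edits the printed summaries instead of the derivation, and nothing in the documents suggests that. Years could also be an intermediate step with the conversion to months left unsaid. Finally, no table shell is given, so the presence of duration in Table 2.1 is inferred from its title, and comparability does not rest on that table alone because the SAP also asks for groups comparable on core baseline parameters and adjusts for duration.

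Most of this stands as an argument about weight, and it keeps the point minor. It does not remove the error. A prespecified derivation should be correct as written and should not depend on someone noticing a strange output. The unit conflict is not self-revealing in the same way, and the SAP does not tell a programmer which unit is meant.

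**Conclusion.** The concern holds. Followed literally, the formula gives a negative duration for every patient diagnosed more than one day before consent (-9.996 instead of +10.001 years for a 10-year history), and the unit is inconsistent by a factor of 12. Apart from the standard deviation and the count, the statistics prescribed for this variable would be wrong.

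The consequence is confined to descriptive output: Table 2.1 and, if it carries the derived value, Listing 2.1. The adjusted comparison between groups is unaffected, provided that duration enters the models as a continuous linear term; the SAP describes no categorization. A duration coefficient, if one were reported, would have the wrong sign, but the SAP does not promise to report one. This is a minor correction, stated with high confidence.

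**What to change.** In SAP section 10, change the derivation to (consent date - diagnosis date + 1) / 365.25. Then settle the unit: either relabel the list item in years, or keep months and state that the result is multiplied by 12. Use the chosen unit in Table 2.1, in Listing 2.1 if duration appears there, and in the model covariate.

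The cost is one line of SAP text, one unit label and the matching program line. Data collection and the planned models do not change.
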